**Clinical Congestion Score** 

Biomarkers

- 3. Brain natriuretic peptide, troponin
- 4. Growth factors (FGF, VEGF)

## 4.3 Safety Plan

The safety of subjects will be carefully monitored and reviewed by an independent Data and Safety Monitoring Board (DSMB).

## 4.4 Compliance with Laws and Regulations

This study will be conducted in accordance with the International Conference on Harmonisation (ICH) E6 Guideline for Good Clinical Practice (GCP), the Declaration of Helsinki (October 1996) and applicable local, state, and federal laws, as well as other applicable country laws.

## 5 STUDY ENROLLMENT

Subjects will participate in this study for 180 days as follows: up to 3±2 days after screening, followed by aMBMC or placebo (LRS) administration, follow-up, crossover phase and follow-up.

## 5.1 Subject Selection

The study will enroll a minimum of 20 subjects and will consist of 2 cohorts. Enrolled subjects will be randomized at 1:1 into an experimental group (n=10) or a placebo group (n=10). Subjects in the experimental group will receive 1.5 million cells per kg and subjects in the placebo group will receive 1 mL/kg Lactated Ringer's Solution. At 90 days the two groups will change arms and the placebo group will receive the stem cell infusion also and the initially treated group will receive a LRS at a volume of 1 mL/kg.

Eligibility will be determined by the inclusion and exclusion criteria listed below.

## INCLUSION CRITERIA

- 1. Males and females ≥18 years of age
- 2. LVEF ≤35% on echocardiogram within 6 months of randomization to undergo MRI
- 3. Screening cardiac MRI at baseline with
  - a. Ejection fraction ≤40%
  - b. No evidence of hyper-enhancement
- 4. Absent or non-obstructive coronary artery disease on x-ray angiography or coronary computed tomography within the past 3 years
- 5. On standard therapy medical therapy (at the discretion of the investigator) including ACE-inhibitors, beta-blockers, and mineralocorticoid receptor antagonists, as tolerated, for at least 3 months
- 6.
- 7. NYHA class II-III symptoms
- 8. Ability to understand and provide signed informed consent
- 9. Reasonable expectation that patient will receive standard post-treatment care and attend all scheduled safety follow-up visits

## **KEY EXCLUSION CRITERIA**

- 1. Pregnant or nursing women or those of childbearing age and not using an effective method of contraception.
- 2. Acute myocardial infarction, acute coronary syndrome, or stroke within 3 months
- 3. Cardiac surgery within 3 months prior to randomization or the likelihood of a requirement for such procedures during the study period
- 4. Current ICD or CRT or implantation planned with 6 months of infusion

- 5. Presence of clinically significant, uncorrected valvular heart disease, hypertrophic or restrictive cardiomyopathy, active myocarditis, or uncontrolled hypertension
- 6. History of cardiac arrest or life-threatening arrhythmias within 3 months
- 7. Treatment with parenteral inotropic agents within 1 month of randomization
- 8. Anticipated cardiac transplantation within 1 year
- 9. Illness other than heart failure with life expectancy less than 1 year
- 10. Received an experimental drug or device within 30 days of randomization
- 11. Left ventricular assist device or implantation planned in the next 6 months
- 12. Patients with complex congenital heart disease
- 13. Uncontrolled seizure disorder.
- 14. Presence of immune deficiency.
- 15. Clinically significant hematologic, hepatic, or renal impairment as determined by screening clinical laboratory tests
- 16. Presence of any other clinically-significant medical condition, psychiatric condition, or laboratory abnormality, that in the judgment of the investigator or sponsor for which participation in the study would pose a safety risk to the subject
- 17. Inability to comply with the conditions of the protocol.
- 18. Malignancy within the previous five years, except basal cell carcinoma, provided that it is neither infiltrating nor sclerosing, and carcinoma in situ of the cervix.
- 19. Active myocarditis or early postpartum cardiomyopathy (within six months).
- 20. Systemic corticosteroids, cytostatics, immunosuppressive drug therapy (cyclophosphamide, methotrexate, cyclosporine, azathioprine, etc.), and DNA depleting or cytotoxic drugs taken within four weeks prior to study treatment.
- 21. Porphyria.
- 22. Allergy to sodium citrate or any "caine" type of local anesthetic.
- 23. Any contraindication for gadolinium use for MRI
- 24. Patient scheduled for hospice care.
- 25. Clinically relevant abnormal findings in the clinical history, physical examination, ECG, or laboratory tests at the screening assessment that would interfere with the objectives of the study or would preclude safe completion of the study. Abnormal findings could include: known HIV infection or other immunodeficiency state, chronic active viral infection (such as hepatitis B or C), acute systemic infections (defined as patients undergoing treatment with antibiotics), gastrointestinal tract bleeding, or any severe or acute concomitant illness or injury.
- 26. Any other medical, social, or geographical factor that would make it unlikely that the patient could comply with study procedures (e.g., alcohol abuse, lack of permanent residence, severe depression, disorientation, distant location, or noncompliance)

#### 5.3 Subject Discontinuation and Withdrawal

Subjects may voluntarily withdraw from the study at any time. In the event of early withdrawal, the reason for withdrawal will be recorded on the appropriate CRF. Attempts to complete early termination exam as defined in 7.4 will be made. The Investigator has the right to discontinue a subject from the study for any medical reason that the investigator determines may jeopardize the subject's safety if he or she continues in the study, or for reasons of noncompliance (e.g., missed visits, use of other investigational drugs, etc.). Each site Investigator may enroll up to 3 additional subjects to each group to offset subjects that are withdrawn or terminated.

## 5.4 Study Termination

The Sponsor has the right to terminate the study at any time. Reasons for terminating the study may include, but are not limited to, the following:

- The incidence or severity of adverse events in this or other studies indicates a potential health hazard to subjects.
- Subject enrollment is unsatisfactory.
- Data recording is inaccurate or incomplete.

## **6** INVESTIGATIONAL PRODUCT

## 6.1 Formulation, Packaging, Preparation, Randomization of aMBMC or Placebo

The study will enroll a minimum of 20 subjects and will consist of 2 cohorts. Enrolled subjects will be randomized at 1:1 into an experimental group (n=15) or a placebo group (n=15). Subjects in the experimental group will receive 1.5 million cells per kg and subjects in the placebo group will receive 1 mL/kg Lactated Ringer's Solution.

Once the subject is randomized into one of the two cohorts, the cells or placebo will be prepared. Within 8 hours of infusion, the appropriate number of cells will be thawed at the study site pharmacy and re-suspended in Lactated Ringer's Solution (LRS) at a concentration of 1x10^6 cells/mL Subjects in placebo group will receive LRS at a volume of 1 mL/kg. The study solution (cells or placebo) will be labeled to indicate that it is an investigational agent and will contain a subject's information, date, and time of formulation.

After discharge, subjects will have safety and efficacy evaluations as per Appendix A.

#### 6.2 IV Administration of aMBMC or Placebo

On the day of infusion, prior to study product administration, a skin test will be administered using 0.1 mL aliquot of the Final Formulation (Appendix C).

An intravenous line will be placed into an appropriate vein on the upper extremity or hand with 0.9% sodium chloride solution running to keep the vein open. The study solution described above will be taken up in an 18-gauge needle into a 60 mL syringe with an eccentric (offset) tip. The needle will be removed and infusion tubing will be attached to the syringe. The syringe with infusion tubing will be placed in a metered dose syringe pump positioned horizontally with the syringe rotated such that the syringe tip is at the lowest position. The product will be infused intravenously into the subject's arm at a constant rate of approximately 2 mL/min. The applicable volume for the target dose will be delivered within  $\pm$  2 mL. Depending on subject's weight, up to three 60 mL syringes of product may be infused. After the entire product volume is delivered, 25 mL of LRS (without cells) will be infused at 2 mL/min to deliver cells from the infusion line for more accurate dosing. Subjects in the placebo group will receive intravenous LRS. Their syringes will be labeled as above to preserve blinding and followed by 25 mL of LRS infusion as above.

If the subject has an adverse reaction during the infusion, the infusion may be interrupted or slowed according to the severity of the reaction. All appropriate treatment will be given to reduce any discomfort and ensure the subject's safety. The infusion may be restarted, if interrupted, if the subject is not considered to be at risk by the Investigator and the subject consents.

All subjects will receive the follow-up tests and evaluations as per Appendix A.

#### 6.3 **Product Storage and Stability**

Once the cell suspension is prepared for administration to a subject as described above, the dose of allogeneic mesenchymal bone marrow cells will be stored at +4°C until the time of administration. All cells will be administered to the subject within 8 hours of preparation. Cells that are not used within this time period will be discarded.

#### 6.4 **Concomitant Medications and Rehabilitation**

Concomitant medications (any prescription and/or over-the-counter preparations) and therapies (nondrug or procedures) used by a subject while participating in this clinical trial will be optimized per AHA Guidelines and recorded at screening and until the end of the study or the end of a subject's participation in the study. Subjects may be administered beta-blockers, ACE inhibitors or angiotensin receptors blockers,

mineralocorticoid receptor antagonists, statin agents, or other medications, as tolerated. All other prescription and over-the-counter preparations approved by the patients' physician will be permitted.

#### 7 STUDY ASSESSMENTS AND SCHEDULE

#### 7.1 **General Assessments**

## **Clinical Assessments**

- Complete medical history, including medication use and lifestyle history •
- Physical and cardiac examination, including vital signs (temperature, systolic blood pressure/diastolic • blood pressure, weight, heart rate, respiratory rate)
- Cardiac Examination •
- Composite of all-cause mortality, admission for worsening HF and all-cause admissions. •
- Exercise capacity: 6 minute walk distance •
- Kansas City Cardiomyopathy Questionnaire (KCCQ)(Appendix B)
- New York Heart Association (NYHA) Classification (Appendix B)

## **Clinical Laboratory Assessments**

- Hematology (CBC): hemoglobin, hematocrit, platelet count, red blood cell count, white blood cell count, automated differential
- Serum Chemistry: includes sodium, potassium, chloride, bicarbonate, blood urea nitrogen (BUN), creatinine, glucose, calcium, phosphorous, total bilirubin, albumin and total protein, and the following liver function tests (LFT's): alkaline phosphatase, alanine aminotransferase (ALT), aspartate aminotransferase (AST)
- Immunoglobulin A (IgA), immunoglobulin E (IgE), immunoglobulin G (IgG), immunoglobulin M (IgM), . and Lymphocyte Proliferation Panel
- Serum Pregnancy test: only for women with child-bearing potential •
- Vascular Endothelial Growth Factor (VEGF)
- Fibroblast Growth Factor (FGF) •
- NT-pro Brain Natriuretic Peptide (NT-proBNP) and cardiac troponin

## ECG

A 12-lead ECG will be performed at all study visits. Standard interval assessments, including QT and QTc, will be calculated from a single lead (typically lead II). QTc will be calculated on the baseline ECG in order to determine if the subject meets enrollment criteria. QTc must be <550ms in order for the subject to be randomized.

## Echocardiography

- A full 2D and Doppler echocardiogram will be performed at screening, at day 90, after initial infusion. After • the crossover phase a full 2D and Doppler echocardiogram will be performed at day 90 after the new infusion.
- Images will be acquired with the patient positioned in the recumbent lateral position. Left ventricular • volumes will be determined at end-diastole and end-systole by quantitative biplane assessment. Endocardial borders will be manually traced from apical four-chamber and two-chamber views. Left ventricular volumes will be used to calculate ejection fraction using the biplane modified Simpson's summation-of-disks method recommended by the American Society of Echocardiography.
- High frame-rate images of the LV in the three apical views (4-chamber, 2-chamber, and apical long axis) • will be acquired for speckle tracking echocardiography. Images will be analyzed offline on a dedicated workstation using EchoPAC BTO 12 (GE Healthcare) software for calculation of segmental and global 19FEB2014

longitudinal strain and strain rate. Global longitudinal strain and strain rate will be calculated from all 18 segments of the LV. Segmental strain and strain rate will be calculated for each segment separately. To assess effect of therapy on impaired regions, we will average strain and strain rate of the dysfunctional segments at baseline and compare the average of these segments over time.

## Cardiac MRI

- Cardiac MRI with gadolinium contrast will be performed at baseline and after 90 days after initial infusion. After the crossover phase an MRI with gadolinium contrast will be performed at new baseline (day 90 after the initial phase) and after 90 days. MRI sequences will include balanced steady state free precession sequence (b\_SSFP) and a delayed contrast enhanced imaging sequence using IV gadolinium contrast, and T2 imaging. Image analysis will be performed by an experienced central laboratory blinded to the subjects' treatment. Efficacy endpoints evaluated by MRI will include: LV end diastolic volume EDV, LV end systolic volume, ESV, and global Left Ventricular Ejection Fraction, and assessment of T2 images for assessing the tissue status
- End-diastolic and end-systolic endocardial traces from contiguous short axis slices will be used to
  determine end-diastolic and end-systolic left ventricular volumes and ejection fraction. Subjects with
  contraindications (e.g. implanted devices, surgical prosthesis, renal impairment or claustrophobia) will not
  undergo MRI.

## Holter monitoring

Those patients who do not have dual chamber defibrillators implanted will undergo twenty four hour Holter monitoring at baseline, day of infusion, at day 30, 60, and 90, after initial infusion and at 30, 60, and 90 days post the new infusion after the crossover phase. For the purposes of this study, life-threatening arrhythmias are defined as ventricular tachycardia (defined as 3 or more consecutive beats arising below the atrioventricular node with a rate >120 beats/min, and complete heart block).

#### Pulmonary Function Tests

Spirometry will be used to assess lung function at screening and at 90 days for the initial phase and at 90 days after the crossover phase. Spirometry tests should be conducted in accordance with the American Association for Respiratory Care (AARC) Spirometry Clinical Practice Guidelines

(www.rcjournal.com/cpgs/spirupdatepg.html). Tests will obtain information about FEV1 (L) and Percent Predicted FEV1. Prior to lung function testing, subjects will be advised to avoid the following activities: 1) Smoking within at least 2 hours of testing, 2) consuming alcohol within 4 hours of testing, 3) vigorous exercise within 4 hours of testing, 4) eating a large meal within 2 hours of testing, 5) consuming caffeine such as coffee, tea, cola drinks, or chocolate on the day of testing.

Diffusing capacity of the lungs for carbon monoxide (DLCO) will also be used to assess lung function at screening and at 90 days. DLCO will be conducted in accordance with the American Thoracic Society and European Respiratory Society guidelines for standardization of the test.

## 7.2 Schedule of Assessments

## 7.2.1 Screening (Day 1-2)

All screening evaluations must be within 1-2 days after identification of possible eligible patients.

- Study participants must meet eligibility criteria (inclusion/exclusion criteria review).
- Signed the written informed consent
- Full 2D and Doppler transthoracic echocardiography with speckle-tracking with LVEF ≤40% If the patient is eligible based on the evaluation above, then
- Complete medical history, including medications history
- Complete physical and cardiac examination, including vital signs (oral temperature, blood pressure, and pulse rate), weight, and height
- 12-lead ECG
- Cardiac MRI, with delayed gadolinium contrast enhancement Subjects with contraindications to MRI because of cardiac devices (pacemakers and defibrillators) will undergo an MRI scan after deactivation

of their device by an electrophysiologist. Other contraindicated patients, e.g. surgical prosthesis, renal impairment or claustrophobia, will not undergo MRI.

- Kansas City Cardiomyopathy Questionnaire (KCCQ)
- New York Heart Association (NYHA) Classification
- Spirometry/DLCO
- Clinical labs: serum chemistry including BUN & creatinine, CBC with diff, LFT's, total protein and albumin,
- Cardiac Biomarkers (CK, CK-MB fraction)
- Pregnancy test, when appropriate
- Serum chemistry
- Serum/plasma stored for VEGF, FGF, NT-proBNP, troponin
- HIV test
- Pulse oximetry
- 24 Hour Holter ECG recording or ICD assessment
- Randomization into experimental or control group
- 6 minute walk test

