#### STUDY TREATMENT

Study subjects will receive infusion at two study sites under the supervision of the site Principal Investigator or qualified co-investigator. Study product administration will be performed  $7 \pm 3$  days after randomization.

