## STATISTICAL METHODS

All randomized subjects who receive at least part of a dose of aMBMC or LRS will be included in the safety analysis. Subject safety data will be analyzed by actual dose level (i.e., number of cells/kg). Adverse events will be coded according to the MedDRA adverse event dictionary. The results will be tabulated to examine their frequency, affected organ systems, severity and relationship to study stem cell administration. The results of laboratory tests will be similarly evaluated. The efficacy analyses will include subjects that received the full dose of aMBMC or LRS and have the appropriate follow-up completed at the scheduled assessments (i.e., efficacy evaluable population). Safety measures include the composite of all-cause mortality, admission for worsening HF and all-cause admissions. Measurement of left ventricle end diastolic volume, left ventricle end systolic volume, left ventricular ejection fraction (LVEF), longitudinal strain and strain rate, global and segmental strain and strain rate, exercise capacity by 6 minute walk distance test, biomarkers, Kansas City Cardiomyopathy Questionnaire (KCCQ) and the New York Heart Association (NYHA) Classification will be completed in the entire efficacy evaluable population. A formal statistical analysis plan will be conducted in accordance with the guidelines of Good Clinical Practice (GCP), including the archiving of essential documents.

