#### 4 STUDY DESIGN

#### 4.1 Description of the Study

This is a Phase IIa, single-blind, placebo-controlled, crossover, multi-center, randomized study in subjects with N-IHF. Within 3 ±2 days all study participants who meet the eligibility criteria will receive the treatment.

The study will enroll a minimum of 20 subjects and will consist of 2 cohorts. Enrolled subjects will be randomized at 1:1 into an experimental group (n=10), or a placebo group (n=10). Subjects in the experimental group will receive 1.5 million cells per kg and subjects in the placebo group will receive 1 mL/kg LRS. At 90 days the two groups will change arms and the placebo group will receive 1.5 million cells per kg and the initially treated group will receive a Lactated Ringer's Solution (LRS) at a volume of 1 mL/kg.

After discharge, subjects will have safety evaluations per Appendix A. Adverse events, concomitant medications, and assessments will be recorded at each follow-up visit. Complete examinations will be used to assess disability and functional status at baseline (prior to treatment), and at the visits scheduled at 30, 60, and 90, after the initial administration. The same process will be followed at visits scheduled at 30, 60, and 90 days after the new administration (crossover phase). A baseline magnetic resonance imaging (MRI) with delayed contrast enhancement and T2 imaging, as well as a full 2D and Doppler transthoracic echocardiography with speckle-tracking will be performed at baseline and at specific time points during follow-up. All performed MRIs will be assessed in a blinded core lab.

Subjects will continue all of their regular medications unless contraindicated. Subjects may be administered beta-blockers, ACE inhibitors or angiotensin receptors blockers, mineralocorticoid receptor antagonists, statin agents, or other medications, as tolerated. Protocol: STEM-104-M-CHF 16 19FEB2014

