## 7.2.2 Assessments and Treatment

## Day 7 ± 3 Days (day of infusion)

#### Pre-infusion:

- Inclusion/exclusion criteria review.
- Review and record any changes in medical history, including concomitant medications from screening.
- Confirm Informed Consent Form (ICF) is complete with signature of subject, or legal guardian & witness.
- Measure and record weight and vital signs (oral temperature, blood pressure, pulse rate) after subjects rest quietly in a supine or semi-recumbent position.
- Final Formulation Skin Test. Performed prior to infusion (Appendix C)
- Physical and Cardiac Examination
- Draw and store blood samples for IgA, IgE, IgG, IgM and for Lymphocyte Proliferation Panel
- Place an IV line in the upper extremity or hand with 0.9% sodium chloride running to keep the vein open

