#### 9.1 Randomization

Once eligibility and consent are confirmed, participants will be randomly assigned to the experimental or placebo group in a 1:1 allocation ratio, stratified by site. At 90 days the two groups will change arms and the placebo group will receive the stem cell infusion and the initially treated group will receive a LRS at a volume of 1 mL/kg.

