#### Procedure to be performed prior to infusion:

Testing is usually done on the volar surface of the forearm or lateral surface of the upper part of the arm.

1. Intradermal test: raise a bleb by intradermal injection using the 0.1 mL of aliquot. Read the test results at 10-15 minutes. A positive result disqualifies the subject.

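### Subjects can be excluded between randomisation and infusion, by a second eligibility review or by a skin test with the allocated product, and no analysis set keeps them

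*Combined protocol and SAP*

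**What the plan says.** **Order of events.** Section 9.1 places allocation after an eligibility check: "Once eligibility and consent are confirmed, participants will be randomly assigned to the experimental or placebo group". Section 7.2.1 is consistent with this. Its list opens with an inclusion/exclusion review and has "Randomization into experimental or control group" near the end, at Day 1-2. Appendix A also puts randomisation at Visit 1. Section 7.2.2 then starts the pre-infusion list for Day 7 ± 3 with "Inclusion/exclusion criteria review".

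**Interval.** Under Study Treatment the synopsis says "Study product administration will be performed" 7 ± 3 days after randomisation. Section 4.1 says that within 3 ± 2 days "all study participants who meet the eligibility criteria will receive the treatment", and Section 5 uses 3 ± 2 days after screening.

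**Skin test.** Section 6.1 prepares cells or placebo once the subject is randomised. Section 6.2 takes 0.1 mL of that final formulation for a skin test before infusion. Appendix C says of this test: "A positive result disqualifies the subject". Section 7.3 and Appendix A repeat the test at Day 90, before the crossover infusion.

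**Analysis sets.** The synopsis defines the safety set: "All randomized subjects who receive at least part of a dose of aMBMC or LRS will be included". The efficacy set (synopsis and Section 9.3) requires the full dose plus follow-up assessments. Section 9 tabulates by treatment actually received. No set of all randomised subjects is defined.

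**Blinding and replacement.** The trial is called single-blind, and the blinded party is not named. Section 5.3 lets each site investigator add up to 3 subjects to each group to offset withdrawals and terminations.

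**The concern.** A between-group comparison is protected by randomisation only while the randomised groups stay intact. Here subjects can leave after allocation and before any infusion, by two routes.

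The first is the repeat eligibility review. Exclusions 16 and 26 rest on judgement (a condition thought to pose a risk; a factor thought to make compliance unlikely). If the person applying them knows the arm, that knowledge can influence who is kept.

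The second is the skin test. The test material is the allocated product, so cells are tested in one arm and LRS in the other. Any difference in reactivity removes subjects unequally, whoever is blinded.

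Neither kind of loss need appear in a planned table. For a trial whose primary objective is safety, a subject disqualified by a reaction to the product is one that the report should show.

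**Working it through.** The plan gives no power calculation or exclusion rate to reproduce (Section 9.4 says that the sample size is not based on power). The check is therefore of sequence and set membership, with two illustrations of scale.

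**1. Gap between randomisation and the second review**

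- Visit labels: Day 7 ± 3 is Day 4 to Day 10. Shortest gap 4 − 2 = 2 days; longest 10 − 1 = 9 days.
- Synopsis, Study Treatment: 7 ± 3 days after randomisation, so 4 to 10 days.
- Sections 4.1 and 5: 3 ± 2 days, so 1 to 5 days if that window is applied.

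The three do not agree and must be reconciled. On every reading there is a gap after allocation.

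**2. Set membership**

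| Subject | Safety set | Efficacy set |
|---|---|---|
| Randomised, fails the repeat review, not infused | Out | Out |
| Randomised, positive first skin test, not infused | Out, unless 0.1 mL counts as part of a dose | Out |
| Infused once, positive skin test at Day 90 | In | Unclear for the second period |

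Adverse event reporting starts after study treatment begins (Section 8.2.1), so it is also unclear whether a positive first skin test would reach the adverse event tables.

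**3. Size of one loss**

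With 10 per arm, 1/10 = 10% of the arm. Sections 5.2 and 6.1 also print group sizes of 15, for which it would be 1/15 = 6.7%. Replacement can mask the loss: 3 subjects × 2 sites = 6 per group, against 10 planned.

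**4. How likely is at least one loss?**

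The pre-infusion exclusion rate p is an assumption. With 20 randomised, expected losses are 20p and P(at least one) = 1 − (1 − p)^20.

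| p | Expected losses | P(at least one) |
|---|---|---|
| 2% | 0.4 | 33% |
| 5% | 1.0 | 64% |
| 10% | 2.0 | 88% |
| 15% | 3.0 | 96% |

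**5. How far could selective loss move an arm mean?**

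In 400,000 simulated samples of 10 standard normal values, with no treatment effect, dropping the lowest 1, 2 or 3 raised the mean of the rest by 0.17, 0.32 or 0.46 SD. This is a ceiling. It assumes that the excluded subjects are exactly those with the worst outcomes, which nobody can know before infusion. The shift shrinks with the correlation between the reason for exclusion and the outcome, and is zero if they are unrelated.

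**The case against.** A pre-dose re-check is ordinary good practice, and the protocol does not say what follows if a subject fails it. Endpoints are described as blinded, MRI is read by a blinded core laboratory, and syringes are labelled to preserve blinding. Section 5.3 records the reason for early withdrawal, and a detailed SAP is still to be written. Section 9 calls the analyses descriptive, and a safety set limited to dosed subjects is a natural choice.

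Much of this is fair. Four stronger readings are tempting, and the documents do not support them:

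- **That Section 9.1 contradicts Section 7.2.1.** It does not: both put an eligibility review before randomisation. The issue is the second review.
- **That staff know the allocation at the second review.** This is not stated. Single-blind status, an unnamed blinded party and replacement by group at the site make it possible. Labelling does not settle it: 1.5 million cells/kg at 1 million cells/mL is 1.5 mL/kg, against 1 mL/kg of LRS, so the volumes differ as written.
- **That exclusion 25 also gives latitude on infusion day.** It is limited to findings at the screening assessment. Only exclusions 16 and 26 support the point.
- **That moving randomisation solves the problem.** It cannot remove the skin-test exclusion, which needs the prepared product.

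Exclusion after a failed re-check, and its replacement under Section 5.3, are inferences. Skin-test disqualification is explicit. Recording a reason on the CRF is not a plan to report losses by arm, and no set definition now requires it. The descriptive label does not remove the concern, because Section 9.2 plans Fisher and ANCOVA comparisons and Section 9.3 an MMRM comparison of the groups.

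**Conclusion.** The point holds in a limited form and should be acted on. After randomisation the plan has one implied route to exclusion before infusion (the repeat review) and one written route (the skin test). Subjects lost by either route are outside the efficacy set. They are outside the safety set as well, unless a skin test counts as part of a dose. Each loss is 10% of an arm of 10.

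That bias would occur is not shown. It requires either knowledge of the arm at the second review, which the documents leave open, or a difference in skin-test positivity between products, for which they give no rate. The probabilities and mean shifts above rest on assumed rates and a worst-case selection rule. The exploratory aim limits the impact, but the planned between-group comparisons mean that it is not nil.

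**What to change.** 1. **Move randomisation to the infusion visit**, after the pre-infusion eligibility review and before product preparation. Subjects who fail that review then become screen failures, not randomised losses. This fits Section 6.1, which prepares product only after randomisation and thaws cells within 8 hours of infusion. Change Section 7.2.1, the Appendix A randomisation row and the synopsis sentence that counts infusion from randomisation. Reconcile the 7 ± 3 and 3 ± 2 day windows; which is intended is for the sponsor to settle.
2. **Define an all-randomised set.** The skin test has to stay after randomisation, so this set is needed in any case. Tabulate every subject randomised but not infused by assigned arm with the reason, including skin-test disqualification. List separately those disqualified at the Day 90 crossover test.
3. **Close the definitions.** State whether the 0.1 mL test counts as part of a dose, and name the blinded party.
4. **Count replacements in addition to**, not in place of, the subjects they follow.

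The cost is protocol and SAP wording plus one table. The site pharmacy would get same-day notice of allocation; the documents do not show whether both sites can work to that, so it should be confirmed. Criteria timed from randomisation (the echocardiogram, cardiac surgery, inotropes, experimental treatments) would shift by the few days of the gap and should be re-read for that reason.
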